### 8.3.2. Outcome definitions

#### 1. Algorithm of outcome definitions

- Hospitalization due to CAP which occurs 1 day or more after the index date. Admission date will be treated as the first day of hospitalization due to CAP.

Hospitalization due to CAP during follow-up period (defined in 8.1 Study Design) will be identified using DPC data. ICD-10 codes, DPC disease segments, prescription data and diagnostic imaging data will be used as follows.

#### Definition 1

- 1) Any of the ICD-10 codes of J10.0, J11.0 or J12-J18
- 2) The above ICD-10 codes in DPC disease segment #21 (disease which triggered the hospitalization)
- 3) Prescription of antibiotics (ATC code: J01) on the day of admission or the next day of hospitalization
- 4) Diagnostic imaging (X-ray or computerized tomography (CT) scan) conducted between 2 days before and 7 days after the hospitalization

#### Definition 2 (for supplemental analysis only)

- 1) Any of the ICD-10 codes of J10.0, J11.0 or J12-J18
- 2) The above ICD-10 codes in DPC disease segment #21 (disease which triggered the hospitalization)
- 3) Prescription of antibiotics (ATC code): J01, dosage form code:4(injection) on the day of admission or the next day of hospitalization
- 4) Diagnostic imaging (X-ray or computerized tomography (CT) scan) conducted between 2 days before and 7 days after the hospitalization

If all of the above 1), 2), 3) and 4) are recorded on the same hospitalization, it is defined as “hospitalization due to CAP”. Medical/medical care-related pneumonia will be included if it meets the outcome definition. Although the JRS guideline recommends the use of injectable antibiotics, we considered that there might be a few patients who received oral antibiotics for the treatment of CAP. Therefore, in definition 1, we use oral antibiotics as well as injectable antibiotics to include those patients who were hospitalized due to CAP and received oral antibiotics. We also use definition 2 focusing on injectable antibiotics to include only patients who were treated according to the guideline.

#### 2. Reasons for setting “hospitalization due to CAP” as the outcome

We set “hospitalization due to CAP” as the outcome measure by the following reasons.

- 1) High accuracy: We can identify “hospitalization due to CAP” in the MDV database with high accuracy, while outpatients due to pneumonia and hospital-acquired pneumonia (HAP) are difficult to identify accurately in MDV database.
- 2) Appropriateness: To evaluate the occurrence of more severe condition of pneumonia, “hospitalization due to CAP” can meet the study objective.

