### 3. Rationales for algorithm of outcome definition

Rationales for the algorithm of outcome definitions are as follows.

- 1) We can identify “hospitalization due to CAP” in MDV database with high accuracy by referring to DPC disease segments. DPC disease segment #1 (disease with the greatest resource utilization), #11 (main disease) and #21 (disease which triggered the hospitalization) are mandatory fields and always specified in every DPC claims. Ando et al. reported high positive predictive value in identifying cases with acute myocardial infarction in DPC claims data by using information of DPC disease segment #1, #11 and #21.
- 2) For the purpose of identifying “hospitalization due to CAP” in this study, we can focus on information of DPC disease segment #21 among the 3 codes, since disease names other than pneumonia can be recorded in the segment #1 if its resource use is greater than that for pneumonia, and time point of pneumonia diagnosis is unknown if pneumonia is recorded in the segment #11.
- 3) This study will not include HAP as the outcome because DPC disease segments #51-#54 (disease occurred during hospitalization) are not mandatory fields and HAP is not completely recorded in DPC claims.
- 4) Pneumonia recorded on medical receipt data (and not DPC data) will not be included as the outcome in this study because there is no code available for the time of pneumonia onset (presence of pneumonia on admission, or pneumonia onset after admission) to differentiate between CAP and HAP.
- 5) We set up the algorithm of outcome definitions by referring to the JRS Guidelines for the Management of CAP in Adults (JRS 2017). The guideline recommends the use of antibiotics right after the diagnosis, and we included the use of antibiotics on the day or the next day of hospitalization in the algorithm. The guideline also recommends to perform chest X-ray or CT scan for confirming diagnosis, and record of diagnostic imaging (X-ray or CT scan) around the admission date was included in the algorithm.

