### 4. Validation of algorithm of outcome definitions

Since this study does not aim to generate evidence for taking safety assurance measures (e.g. amendment of package insert), no validation study for study outcomes is required by the PMDA (agreed with the PMDA on Sep 20, 2019).

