### 8.5.1. Study Size for HR in primary analysis

In primary analysis, HR for hospitalization due to CAP among incident Trelegy 100 users compared to incident MITT users within the 360-day follow-up period will be estimated along with 95% confidence intervals using Cox proportional hazard model (follow-up period will be up to 360 days in the base-case analysis).

For a relative risk in HR between incident Trelegy 100 users and incident MITT users in real-world data, according to the report, it's stated that "relationships with relative risks varying between 0.5 and 2 are the ones most commonly reported in analyses of real-world data, and are those most susceptible to unaccounted for confounding that can only be addressed with an randomised controlled trials." Also, some key data (ex. lung function test results, respiratory symptoms evaluated by questionnaires and so on) are not available in MDV database, and the difference in the patient characteristics between Trelegy 100 users and MITT users in Japan is not known. Considering these situations, it's reasonable that we won't consider an HR  $\leq$  3 to be a signal.

Given the following combination of sample size, probability of observing HR > 3 is displayed as below. we considered the following patients, as sample size is being projected based on market forecast.

Table 1 Sensitivity based on different hospitalization due to CAP rates, HRs and patients

Incident Trelegy Users	Incident MITT Users	Expected annual hospitalization due to CAP rate (%)	True HR#	Probability of observing HR > 3 (%)
3225	2185	8	2	0.0
			2.5	6.0
			3	50.0
			3.5	88.1
			4	98.2
3225	2185	10	2	0.0
			2.5	4.1
			3	50.0
			3.5	90.7
			4	> 99.0
3225	2185	12	2	0.0
			2.5	2.9
			3	50.0
			3.5	92.6
			4	> 99.0
3225	2185	14	2	0.0
			2.5	2.0
			3	50.0
			3.5	94.1
			4	> 99.0
1935	1311	8	2	0.2
			2.5	11.4
			3	50.0
			3.5	82.0
			4	94.9
1935	1311	10	2	0.1
			2.5	8.9
			3	50.0
			3.5	84.7

			4	96.6
1935	1311	12	2	0.0
			2.5	7.0
			3	50.0
			3.5	86.9
			4	97.7
1935	1311	14	2	0.0
			2.5	5.6
			3	50.0
			3.5	88.7
			4	98.5

Note: Probability of observing HR > 3 using asymptotically normal distribution

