## 8.9. Limitations of Research Methods

This study uses MDV database which consists of hospital data, and thus only patient data in the hospitals included in MDV database are available. If a patient is treated in hospitals outside of MDV database, treatment records are not available. In MDV database, data can be extracted from health insurance claims and DPCs, but some key data (including smoking history, BMI) are not recorded completely. Based on these characteristics of MDV database, there are some limitations listed below:

- Outcome:
  - It is possible that some pneumonia events requiring hospitalization are recorded outside of DPCs, resulting in underestimation of the outcome measure. If pneumonia requiring hospitalization is treated in hospitals outside of MDV database, such data are not available and outcome measure is underestimated.
  - If data in DPC disease segment #21 (disease which triggered the hospitalization) are incorrect, occurrence of CAP will be overestimated or underestimated.
  - Pneumonia identified by only ICD-10 codes may be overestimated. Addition of prescription of antibiotics and imaging diagnosis to the outcome definition can increase the accuracy, but still there may be some overestimation.
- Risk factors for pneumonia:
  - Old age, lower % predicted forced expiratory volume in 1 second (FEV1), history of COPD exacerbations, worse Medical Research Council (MRC) dyspnea score and lower BMI were treatment-independent risk factors for pneumonia. In MDC database, data of lung function and respiratory symptoms are not available, and BMI data are only partially available.
- Exposure:
  - The reason (e.g., transfer, death) is unknown when Trelegy 100 or MITT prescription records are no longer available after the index date if a patient is treated in hospitals outside of the database. In MDV database, there are no records of the reasons for change in prescription. Dosage information is not available for inhaled drugs, and the estimated daily dose and prescription period could be different from the actual ones.
  - In MDV database, treatment adherence data are not available, and the estimated exposure period could be different from the actual one.
- Study population:

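### The CAP endpoint's high accuracy is not supported for pneumonia, and false positives unrelated to treatment would pull the HR towards 1, which 8.9 and Table 1 do not allow for

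*Protocol*

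**What the plan says.** Section 8.3.2, item 2, justifies the endpoint by saying that such admissions can be found "in the MDV database with high accuracy, while outpatients due to pneumonia and hospital-acquired pneumonia (HAP) are difficult to identify accurately". Item 3 repeats the claim and supports it with a study that "reported high positive predictive value in identifying cases with acute myocardial infarction in DPC claims data" using segments #1, #11 and #21. For CAP, item 3 then says that "we can focus on information of DPC disease segment #21 among the 3 codes". It argues that #1 may hold a costlier disease and that #11 does not date the pneumonia. Definition 1 adds an antibiotic on the day of admission or the next day, and imaging around admission.

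Item 4 records that "no validation study for study outcomes is required by the PMDA", on the ground that the study is not meant to support safety measures. The protocol gives no PPV, sensitivity or specificity for pneumonia.

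Section 8.9 allows that segment #21 may be wrong and says: "Addition of prescription of antibiotics and imaging diagnosis to the outcome definition can increase the accuracy, but still there may be some overestimation". It closes by saying that limitations acting on both groups to a similar extent could have little effect on internal validity.

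Section 7 asks whether the HR exceeds 3. Section 8.5.1 says "it's reasonable that we won't consider an HR" of 3 or less to be a signal. Table 1 gives the probability of observing an HR above 3 for true HRs from 2 to 4.

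**The concern.** The cited evidence does not carry over to this endpoint, because both the disease and the set of segments differ. How many counted admissions are not pneumonia is therefore unknown, while the protocol itself accepts that there will be some.

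The direction of the error matters because the decision rule is one-sided. A false positive that has nothing to do with the inhaler adds the same hazard in both groups, so the ratio shrinks towards 1. A study that looks for an HR above 3 is then less likely to see one. Similarity between the groups, which 8.9 offers as reassurance, is the condition under which this dilution occurs. At stake is what an observed HR at or below 3 can support.

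**Working it through.** **Inputs.** Incident users 3225 v 2185 or 1935 v 1311; CAP rate 8%, 10%, 12% or 14% per year; threshold HR 3 (sections 8.5 and 8.5.1). The PPV is not in the protocol and is assumed below.

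**Step 1: reproduce Table 1.** Total events D = rate × (n1 + n0), split between the groups as n1·HR : n0. SE = √(1/d1 + 1/d0). P(observed HR > 3) = Φ[ln(HR/3)/SE].

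For 3225 v 2185, 8%, true HR 3.5:
- D = 0.08 × 5410 = 432.8
- Trelegy 100 share = 11287.5/13472.5 = 0.838, so d1 = 362.6 and d0 = 70.2
- SE = √(1/362.6 + 1/70.2) = 0.130
- ln(3.5/3)/0.130 = 1.18, which gives 88.1%, the printed value

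All 40 cells agree within 0.1 point (the three printed only as above 99.0 come out above 99.0). The calculation contains no term for outcome error, so Table 1 takes the true HR to be the HR that the database shows.

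**Step 2: add false positives.** Let λ1 and λ0 be the true CAP hazards, s a common sensitivity and f a false-positive hazard equal in both groups. Then HR_obs = (sλ1 + f)/(sλ0 + f). With PPV = sλ0/(sλ0 + f) in the MITT group, this becomes

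HR_obs = PPV × HR_true + (1 − PPV).

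Equal sensitivity below 1 cancels; false positives do not. Setting HR_obs = 3 gives HR_true = [3 − (1 − PPV)]/PPV. At PPV 0.80 this is (3 − 0.20)/0.80 = 3.50.

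**Step 3: size over an assumed PPV range.** Probabilities use the Step 1 formula at the diluted HR, keep the overall observed rate at 8% to 14%, and span all eight scenarios.

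| MITT-group PPV (assumed) | True HR behind an observed 3 | Observed HR when true HR is 3.5 | P(observed > 3), true HR 3.5 | P(observed > 3), true HR 4 |
|---|---|---|---|---|
| 1.00 (Table 1) | 3.00 | 3.50 | 82.0–94.1% | 94.9–99.7% |
| 0.95 | 3.11 | 3.375 | 76.1–88.7% | 92.4–99.3% |
| 0.90 | 3.22 | 3.25 | 68.7–79.7% | 88.9–98.2% |
| 0.80 | 3.50 | 3.00 | 50.0% | 77.4–90.0% |
| 0.70 | 3.86 | 2.75 | 17.0–28.8% | 58.0–63.5% |

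**Step 4: which PPV is meant.** The formula needs the MITT-group PPV. If the figure at hand is pooled over both groups (3225 : 2185, observed HR 3), the false-positive share of the MITT hazard is (1 − P)(3 × 3225 + 2185)/5410. For a pooled P of 0.90 this is 0.219, and the true HR is (3 − 0.219)/(1 − 0.219) = 3.56 rather than 3.22.

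**Step 5: false positives that differ by group.** In general HR_obs = PPV × HR_CAP + (1 − PPV) × HR_FP. At PPV 0.80 and an observed HR of 3, HR_CAP is (3 − 0.16)/0.80 = 3.55 if HR_FP is 0.8, and (3 − 0.40)/0.80 = 3.25 if HR_FP is 2. At the threshold the direction reverses only if HR_FP exceeds 3.

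**The case against.** The endpoint is not built on the myocardial infarction study alone. Segment #21 is mandatory and names the disease that triggered admission, and early antibiotics and imaging are also required. Section 8.9 discloses both coding error and residual overestimation, and its closing sentence is conditional and asks for careful interpretation. The regulator agreed that no validation study was needed. These points stand as reasons why the PPV might be good, but none supplies one. The disclosure is undercut by a closing sentence that treats shared error as nearly harmless.

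A reader might infer that the protocol cannot tell CAP from a COPD exacerbation, because the look-back exacerbation definition in 8.3.3.1 accepts the same pneumonia codes. The documents do not go that far. The outcome list leaves out J44.1, J20–J22 and J96.1, and the exacerbation definition also requires a systemic corticosteroid. The overlap shows that one admission can meet both definitions, not that exacerbations are counted as CAP.

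Nor is Definition 2, which narrows only the antibiotic route, the sole variation on the outcome. Section 8.7.3 adds a supplemental analysis without COVID-19-coded events, 8.7.3.2.1 splits incidence rates by type of imaging, and the data review is to confirm the CAP definition. None of these tests the choice of segment or yields a PPV.

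Finally, 8.5.1 chose 3 deliberately, with confounding in mind, and a bias analysis should not reset it. Requiring the conclusion to hold down to a PPV of 0.6 would mean an observed HR of at most 1 + 0.6 × 2 = 2.2. With a perfectly measured outcome (3225 v 2185, 8%), a true HR of 2.5 would fail that rule about 86% of the time. That objection is accepted.

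**Conclusion.** The concern holds in a limited form. High accuracy is not established for pneumonia, and the last sentence of 8.9 is wrong for false positives that arise alike in both groups. Such errors bias the HR towards 1 and so weaken a conclusion that it is not above 3. Table 1 assumes that they are absent.

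It is tempting to say that an observed HR of 3 means a true HR well above 3. The documents do not support that, since they contain no PPV. At a MITT-group PPV of 0.95 to 0.90 the true HR is only 3.1 to 3.2; it reaches 3.5 at 0.80 and 3.9 at 0.70. At 0.80 the chance of flagging a true HR of 3.5 falls to 50%, from 82.0% to 94.1%. These figures rest on the assumed PPV and on false positives unrelated to treatment.

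**What to change.** 1. **Section 8.3.2, items 2 and 3.** Do not present high accuracy as established. Say that the PPV for pneumonia is unknown.
2. **Section 8.7.3.** Add a supplemental analysis of the primary HR that requires the pneumonia code in #21 and also in #1 or #11, with the same antibiotic and imaging criteria. Segment #21 still dates the pneumonia to admission, and all three fields are mandatory. Some sensitivity is lost, but an equal loss in both groups does not materially bias the HR.
3. **Section 8.7.3.** Beside the primary HR, report a bias table over a stated range of MITT-group PPV: HR_CAP = [HR_obs − (1 − PPV) × HR_FP]/PPV, with the same transformation applied to each confidence limit. Use HR_FP = 1 as the base case and show other values.
4. **Section 8.9, last sentence.** State that false positives similar in both groups bias the HR towards 1 and weaken a conclusion that it is not above 3.

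Keep the threshold of 3, and do not require the conclusion to hold across the whole table.

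The cost is one more outcome flag from data already extracted, one table and two text edits, with no validation study. The supplemental analysis will have fewer events, and a no-signal conclusion will be more qualified.

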### 3. Rationales for algorithm of outcome definition

Rationales for the algorithm of outcome definitions are as follows.

- 1) We can identify “hospitalization due to CAP” in MDV database with high accuracy by referring to DPC disease segments. DPC disease segment #1 (disease with the greatest resource utilization), #11 (main disease) and #21 (disease which triggered the hospitalization) are mandatory fields and always specified in every DPC claims. Ando et al. reported high positive predictive value in identifying cases with acute myocardial infarction in DPC claims data by using information of DPC disease segment #1, #11 and #21.
- 2) For the purpose of identifying “hospitalization due to CAP” in this study, we can focus on information of DPC disease segment #21 among the 3 codes, since disease names other than pneumonia can be recorded in the segment #1 if its resource use is greater than that for pneumonia, and time point of pneumonia diagnosis is unknown if pneumonia is recorded in the segment #11.
- 3) This study will not include HAP as the outcome because DPC disease segments #51-#54 (disease occurred during hospitalization) are not mandatory fields and HAP is not completely recorded in DPC claims.
- 4) Pneumonia recorded on medical receipt data (and not DPC data) will not be included as the outcome in this study because there is no code available for the time of pneumonia onset (presence of pneumonia on admission, or pneumonia onset after admission) to differentiate between CAP and HAP.
- 5) We set up the algorithm of outcome definitions by referring to the JRS Guidelines for the Management of CAP in Adults (JRS 2017). The guideline recommends the use of antibiotics right after the diagnosis, and we included the use of antibiotics on the day or the next day of hospitalization in the algorithm. The guideline also recommends to perform chest X-ray or CT scan for confirming diagnosis, and record of diagnostic imaging (X-ray or CT scan) around the admission date was included in the algorithm.

### 4. Validation of algorithm of outcome definitions

Since this study does not aim to generate evidence for taking safety assurance measures (e.g. amendment of package insert), no validation study for study outcomes is required by the PMDA (agreed with the PMDA on Sep 20, 2019).

### 5. Evaluation of outcomes in this study

A patient will be censored at the first event of “hospitalization due to CAP,” because identification of “time at risk for pneumonia” is feasible for the first event but difficult for the second or subsequent events. For example, if hospitalization due to CAP continued longer than the recovery from CAP by another comorbidities, it is not clear when the patient recovered from CAP during the hospitalization. Namely, “the end date of the current pneumonia” and thus “time at risk for the next pneumonia” cannot be identified.

### 6. Consideration of COVID-19 pandemic

Index dates for starting triple therapy will be between May 22, 2019 and May 5, 2022 including the period of the COVID-19 pandemic. Effects of the COVID-19 pandemic on the results will be described according to the GSK internal guidance for retrospective database studies.

“Hospitalization due to CAP” will be classified into with or without disease code for COVID-19 in the same hospitalization record.

- DPC disease segment #21 (disease which triggered the hospitalization): ICD-10 codes for pneumonia for all cases
- DPC disease segments other than #21 (primary disease, comorbidities at admission, etc.): with or without disease code for COVID-19

Detailed methods for identifying pneumonia cases in COVID-19 infected patients will be defined later in the analysis plan when a medical recording method for the case is generalized.

If COVID-19 infection is the disease with the greatest resource utilization (i.e. applicable to DPC

disease segment #1), diagnosis in the same hospitalisation are recorded on medical receipt data (not DPC claim data). Therefore we cannot identify “Hospitalization due to CAP” in DPC claim data if patients have COVID-19 infection and COVID-19 infection is the disease with the greatest resource utilization throughout the hospitalisation.

Record of COVID-19 testing during “hospitalization due to CAP” will be collected. If the test result is positive, “confirmed disease code for COVID-19” will be recorded. Higher rate of testing could be indicative for robustness of the proportion of COVID-19 infection among “hospitalization due to CAP”.

### 8.3.3. Confounders and effect modifiers

#### 8.3.3.1. Covariates

The following covariates data will be used to calculate the marginal HR for hospitalization due to CAP among incident Trelegy 100 users compared to incident MITT users (primary objective), to characterize target patients (secondary objective-b) and to calculate adjusted HRs for “hospitalization due to CAP” among subgroups within Trelegy 100 or MITT groups (secondary objective-c)).

- **Sex**
- **Age:** Age at index date
- **Calendar year of index date:** Because medical practice changes over time
- **Month of index date (and not the month of hospitalization due to CAP):** Because of seasonal differences in pneumonia occurrence
- **COPD treatments in look-back period**
  - 1) Immediate previous treatment as COPD maintenance therapy (LAMA, LABA, LAMA/LABA, ICS/LABA, ICS/LAMA/LABA or no COPD maintenance therapy): As potential confounding factors
    - Immediate previous therapy will be identified during 180 days before the index date (and not during the entire look-back period).
  - 2) Prescriptions of ICS as treatment of COPD or asthma: As a risk factor for pneumonia occurrence during the look-back period  
Confirm that ICD-10 code for COPD (J42, J43 or J44) or asthma (J45 or J46) is recorded in the receipt of the month which includes prescription of ICS.
  - 3) Prescriptions of oral corticosteroid (OCS) as treatment of COPD or asthma: As a risk factor for pneumonia occurrence during the look-back period  
Confirm that ICD-10 code for COPD (J42, J43 or J44) or asthma (J45 or J46) is recorded in the receipt of the month which includes prescription of OCS.
  - 4) Home oxygen therapy (HOT) for COPD: As an index for COPD severity  
Confirm that ICD-10 code for COPD (J42, J43 or J44) is recorded in the receipt of the month which includes the conduct of HOT.
    - Other therapies (including rescue therapy, xanthine, biologicals) for COPD or asthma will not be included as covariates.

- **History of COPD exacerbation**

In MDV database, hospitalization due to COPD exacerbation (severe COPD exacerbation) will be identified correctly by using DPC data, while it is difficult to identify mild/moderate COPD exacerbation without hospitalization (i.e., without DPC data) because systemic corticosteroids/antibiotics are prescribed for various diseases and prescription data are not linked with disease data one by one.

Hospitalizations due to COPD exacerbation in the look-back period.

- Definition: Hospitalization due to COPD exacerbation in the look-back period will be identified using DPC data. The following ICD-10 codes, DPC disease classification codes and prescription data will be used.
  - 1) Any of the following ICD-10 codes as DPC disease segment #21 (disease which triggered the hospitalization)
    - Pneumonia-related codes: J10.0, J11.0, J12-J18
    - Acute lower respiratory tract infection-related codes: J20-J22
    - COPD exacerbation-related codes: J44.1
    - Chronic respiratory failure: J96.1
  - 2) Prescription of any systemic corticosteroid combined with any systemic antibiotics at the admission day or the next day. Date of prescription with systemic corticosteroid can be the same as or different from that of antibiotics prescription.

If both of the above 1) and 2) are recorded on the same hospitalization, it is defined as “COPD exacerbation requiring hospitalization”.

Only the presence or absence of the event in the look-back period will be identified.

- **History of pneumonia**

Hospitalization due to CAP in the look-back period

- Definition: Same definition as the outcome measure (see “Sec 8.3.2 Outcome definitions”)
- Only the presence or absence of the event n look-back period will be identified.

■ **Medical history or comorbidities**

The following medical history or comorbidities in the look-back period

- Definition:  $\geq 1$  record (outpatient visit or hospital admission) with relevant ICD-10 codes for each comorbidities in the look-back period [Index date – 360 days]
  - 1) Asthma (ICD-10 codes: J45, J46)
  - 2) Myocardial infarction (ICD-10 codes: I21.x, I22.x, I25.2)
  - 3) Congestive heart failure (ICD-10 codes: I09.9, I11.0, I13.0, I13.2, I25.5, I42.0, I42.5-I42.9, I43.x, I50.x, P29.0)
  - 4) Cerebrovascular disease (ICD-10 codes: G45.x, G46.x, H34.0, I60.x-I69.x)
  - 5) Dementia (ICD-10 codes: F00.x-F03.x, F05.1, G30.x, G31.1)
  - 6) Peptic ulcer (ICD-10 codes: K25.x-K28.x)
  - 7) Peripheral vascular disease (ICD-10 codes: I70.x, I71.x, I73.1, I73.8, I73.9, I77.1, I79.0, I79.2, K55.1, K55.8, K55.9, Z95.8, Z95.9)
  - 8) Connective tissue disease (ICD-10 codes: M05–M08, M30–M36)
  - 9) Diabetes (ICD-10 codes: E10.0-E10.9, E11.0-E11.9, E12.0-E12.9, E13.0-E13.9, E14.0-E14.9)
  - 10) Anxiety (ICD-10 codes: F40-F42)
  - 11) Depression (ICD-10 codes: F32, F33)
- Data of medical history/comorbidity of asthma will be collected by the definition using both ICD-10 codes and prescription data, in addition to the definition using only ICD-10 codes.

Definition:  $\geq 1$  records of visits (outpatient visit or hospital admission) with ICD-10 codes (J45, J46) and  $\geq 1$  records of prescriptions of at least one of ICS, ICS/LABA or leukotriene receptor antagonist (LTRA)

■ **BMI**

BMI will be calculated by body weight and height. Data of body weight and height are available from hospitalization records (DPC data or medical receipt data). If a study participant is hospitalized by any reasons in the look-back period, BMI data can be available from the hospitalization record.

■ **Smoking history**

Smoking history data are available from hospitalization records (DPC data or medical receipt data). If a study participant is hospitalized by any reasons in the look-back period, smoking history data can be available from the hospitalization record.

■ **Lung function test**

Presence or absence of lung function test in the look-back period. Lung function test results are not available but Yes/No of conducting lung function test are recorded in MDV database.

The following covariates have been considered in previous studies which had evaluated the association between ICS treatment and pneumonia occurrence among COPD patients. These covariates are baseline characteristics of study population and a certain length of time close to the period with exposure (Trelegy 100 or MITT) will be needed to collect data. Therefore we will collect these covariate data in the 360 days before the index date (look-back period).

■ **COPD treatments in the look-back period**

- 1) Immediate previous treatment as COPD maintenance therapy (LAMA, LABA, LAMA/LABA, ICS/LABA, ICS/LAMA/LABA or no COPD maintenance therapy)
- 2) Prescriptions of ICS as treatment of COPD or asthma: As a risk factor for pneumonia occurrence
- 3) Prescriptions of OCS as treatment of COPD or asthma: As a risk factor for pneumonia occurrence

- History of COPD exacerbation
- History of pneumonia
- Medical history or comorbidities
  - 1) Asthma
  - 2) Myocardial infarction
  - 3) Congestive heart failure
  - 4) Cerebrovascular disease
  - 5) Dementia
  - 6) Peptic ulcer
  - 7) Peripheral vascular disease
  - 8) Connective tissue disease
  - 9) Diabetes
  - 10) Anxiety
  - 11) Depression
- BMI
- Smoking history

